##### **13.2.1.3. Safety Population**

The safety population will consist of all patients who have received at least one dose of study treatment and have any post-baseline safety information.

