
Methodology:
 
This is a Phase 2b, single-arm, open-label, multicenter study of Sd, dosed twice weekly each week in four-week cycles, in patients with penta-refractory MM (Parts 1 and 2) or quad-refractory MM (Part 1 only).
 
The population for the primary efficacy analysis will contain only patients with penta-refractory MM enrolled in Part 2. Response results for patients with quad-refractory MM and patients with penta-refractory MM enrolled in Part 1 will be analyzed separately. Safety analyses will be performed on the overall population of patients who received at least one dose of study drug, presented overall and by study part, and separately for Part 1 penta-refractory and quad-refractory patient populations.
 
Patients will receive treatment until progressive disease (PD), death, toxicity that cannot be managed by standard care, or withdrawal, whichever occurs first.
		

Inclusion/Exclusion Criteria:
 
Inclusion:
		

Sponsor: Karyopharm Therapeutics Inc.	Investigational Product: Selinexor (KPT-330)	Developmental Phase: Phase 2b

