## 12.1. Serious Adverse Events

A serious adverse event (SAE) is any untoward medical occurrence that occurs at any dose (including after the ICF is signed and prior to dosing) that:

- Results in death
- Is life-threatening (patient is at immediate risk of death from the event as it occurred)
- Requires in-patient hospitalization (formal admission to a hospital for medical reasons) or prolongation of existing hospitalization
- Results in persistent or significant disability/incapacity
- Results in a congenital anomaly/birth defect

Important medical events that may not result in death, are not life-threatening, or do not require hospitalization may be considered SAEs when, based on appropriate medical judgment, they may jeopardize the patient and may require medical or surgical intervention to prevent one of the outcomes listed in this definition. Examples of such events include allergic bronchospasm requiring intensive treatment in an emergency room or at home, blood dyscrasias or convulsions that do not result in in-patient hospitalization, or the development of drug dependency or drug abuse.

Hospitalizations for elective surgery or other medical procedures that are not related to a treatment-emergent AE are not considered SAEs.

Progression of the malignancy (including fatal outcomes) should not be reported as an SAE during the study or within the safety reporting period (see below). Sudden and unexplained death should be reported as an SAE.

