### 13.3.7. Safety Data

Safety analyses will be performed on the overall population of patients who received any amount of study treatment, presented overall and by study part, and separately for Part 1 penta-refractory MM patients, Part 1 quad-refractory MM patients, and Part 2 penta-refractory MM patients. The original dose level for each patient will be used for safety analysis; no separate categories for dose escalation or reduction will be conducted in the primary analysis of safety. CCI [REDACTED]

[REDACTED]

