1. OVERVIEW AND INVESTIGATIONAL PLAN

1.1. STUDY DESIGN

KCP-330-012 is a Phase 2b, single-arm, open-label, multicenter study of Sd (selinexor 80 mg plus dexamethasone 20 mg), both dosed twice weekly, for each week of a four-week cycle, in patients with multiple myeloma (MM) previously treated with alkylating agents, glucocorticoids, lenalidomide, pomalidomide, bortezomib, carfilzomib, and daratumumab, and refractory to prior treatment with glucocorticoids, at least one immunomodulatory agent (IMiD), at least one proteasome inhibitor (PI), and the anti-CD38 mAb daratumumab (i.e., penta-refractory MM). Note: refractory is defined as $\leq 25\%$ response to therapy, progression during the previously described therapies, or progression within 60 days after completion of the therapy (per International Myeloma Working Group [IMWG] criteria 2016).

This study consists of two parts and will enroll approximately 210 patients overall. Part 1 (protocol V1.0-3.0) enrolled patients with both quad-refractory MM (i.e., previously treated with alkylating agents, glucocorticoids, lenalidomide, pomalidomide, bortezomib, carfilzomib, but not an anti-CD38 mAb, and refractory to prior treatment with glucocorticoids, at least one IMiD, and at least one PI) along with patients that had quad-refractory MM and whose disease was refractory to an anti-CD38 monoclonal antibody (i.e., penta-refractory MM). Part 2 (protocol V \geq 4.0) will enroll patients with penta-refractory MM only, and refractoriness to prior treatment with daratumumab (the only currently FDA approved anti-CD38 monoclonal antibody) is required.

The population for the primary efficacy analysis will contain only patients with penta-refractory MM enrolled in Part 2. Efficacy results for patients with quad-refractory MM and patients with penta-refractory MM enrolled in Part 1 will be analyzed separately. Safety analyses will be performed on the Part 2 patients with penta-refractory MM, the overall safety population of patients who received any amount of study treatment, presented together as well as separately by study part.

Patients receive oral selinexor 80 mg plus dexamethasone 20 mg (Sd), both dosed twice weekly, for each week of four-week cycles. Patients will receive treatment until progressive disease (PD), death, toxicity that cannot be managed by standard care, or withdrawal, whichever occurs first.

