3.1.2. Safety Population

The safety population will consist of all patients from Part 1 and Part 2, who have received at least one dose of study treatment (partial or complete) and have any post-baseline safety information.

Safety outputs will be presented by the following groups:

- Overall safety population
- The subset of safety population from Part 2
- The subset of safety population from Part 1

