5. SAFETY

Safety analyses will use the safety population with the outputs presented by the following groups:

- Overall safety population
- The subset of safety population from Part 2
- The subset of safety population from Part 1

Safety analyses will be based on the reported AEs and other safety information, such as 12-lead electrocardiogram (ECG), ophthalmic exam, clinical laboratory assessments including hematology, serum chemistry, coagulation parameters, and urinalysis, vital signs, physical examination, and pregnancy testing.

Observation period

The observation period will be divided into the following periods:

- The pre-treatment period is defined as the time from the signed informed consent date up to first dose of study treatment.
- The treatment period is defined as the time from first dose of study treatment to last dose of study treatment + 30 days inclusive.
- The post-treatment period is defined as the time beyond the treatment period.

The on-study observation period is pre-treatment, treatment, and post-treatment period.

General rules

All safety analyses will be performed using the following common rules:

- Safety data in patients who do not belong to the safety population (e.g., enrolled but did not receive any dose of study treatment, partial or complete) will be listed separately.
- The baseline value is the last available value before the first dose of study treatment.
- The analyses of the safety variables will be essentially descriptive and no systematic testing is planned.

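### The safety population is defined more narrowly in protocol 13.2.1.3 and SAP 3.1.2 than in the sections that plan the safety analyses; the extra condition on post-dose data should go

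*Protocol*

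**What the plan says.** Two descriptions of the safety set stand side by side in the current text.

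**With a condition on post-dose data.** Protocol 13.2.1.3: "The safety population will consist of all patients who have received at least one dose of study treatment and have any post-baseline safety information". SAP 3.1.2 covers patients of both parts "who have received at least one dose of study treatment (partial or complete) and have any post-baseline safety information".

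**Without it.** Protocol 13.3.7: "Safety analyses will be performed on the overall population of patients who received any amount of study treatment". The synopsis (Methodology): "Safety analyses will be performed on the overall population of patients who received at least one dose of study drug". Protocol 7.1, 13.1.1 and 13.3.4 use the same treatment-only criterion. SAP 1.1 goes further and describes "the overall safety population of patients who received any amount of study treatment", so the SAP gives two definitions under the same name.

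Three related rules matter:
- SAP 5.1.2 sets the denominator of adverse event percentages to the size of the corresponding population.
- SAP 3.4 summarises treatment exposure in the safety population.
- SAP 5 (General rules) provides a separate listing for "Safety data in patients who do not belong to the safety population". Its example is patients who were enrolled but never dosed.

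Neither document defines what counts as post-baseline safety information.

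**The concern.** A safety set is normally fixed by exposure alone. Once a patient has taken a dose, whether data were later recorded is part of what happened after dosing, and conditioning on it is selection on a post-treatment outcome. The patients it can remove are those lost very early with nothing recorded afterwards. They would leave the adverse event denominators and the exposure summary while remaining treated patients under every other description in the two documents.

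The study is single-arm, and its primary analysis feeds a clinical study report ahead of a marketing application (SAP 1.6). The safety denominators should therefore not depend on which section a programmer follows. At stake are the clarity of the definition and a small shift in percentages, not the efficacy conclusion.

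**Working it through.** The documents give no count of treated patients without later data, so there is no plan figure to reproduce. The check compares the texts and then bounds the effect.

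**1. Is the conflict resolved anywhere?** No. Both versions are current text, and neither the SAP's list of modifications to the protocol (1.7) nor its own change list (1.8) reconciles them. Two features of the plan favour the broader version:
- The only example in SAP 5 of someone outside the safety population is an undosed patient.
- The per-protocol set (protocol 13.2.1.2, SAP 3.1.3), which also asks for a post-baseline assessment, exempts patients who died or withdrew first. The safety population has no such exemption.

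**2. How could a treated patient be excluded?** The condition is met by any information at any later time. Table 1 of the protocol schedules a mandatory Day 3 call, visits on Days 8 and 15, an end-of-treatment visit within 14 days of the last dose, and a safety call 30 days after it. Exclusion needs all of these to yield nothing.

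**3. Direction and size for adverse events.** A patient with a recorded post-dose event has safety information, so excluded patients contribute no events. With x patients having the event, N treated and k excluded:

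- treatment-only definition: p = x/N
- conditional definition: x/(N − k) = p × N/(N − k)

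Inputs:
- N = 79 + about 130 = about 209 (synopsis, Study Numbers).
- p = 64%, the preliminary rate of treatment-related thrombocytopenia of any grade (protocol 4.3.1.4).
- k = 1 to 4 is assumed.

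Results:
- k = 1: 64% × 209/208 = 64.3%
- k = 4: 64% × 209/205 = 65.2%

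For Part 2 alone, N = 130. With the 51% Grade 3/4 thrombocytopenia rate from the same section, x = 66:
- k = 0: 66/130 = 50.8%
- k = 1: 66/129 = 51.2%
- k = 5: 66/125 = 52.8%

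The exclusion can only raise adverse event percentages.

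**4. Effect on efficacy.** The primary response analysis uses the mITT population (protocol 13.2.1.1, SAP 3.1.1), which requires a dose and eligibility or a waiver but no post-baseline data. It does not change.

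**The case against.** The best defence is that the two formal definitions agree with each other, that the looser phrasing sits in descriptive text, and that almost nobody will be excluded. It can also be said that a sentence defining the term and promising to report the number excluded would serve as well as deletion. On size this stands: the shift is small, it does not hide toxicity, and k is assumed. On the text it does not stand in full. Protocol 13.3.7 is the operative section for the safety analyses, and SAP 1.1 describes the safety population by name without the condition.

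A reader might infer something stronger: that early deaths would vanish from the safety tables. The reasoning would be that protocol 12.1 says "Progression of the malignancy (including fatal outcomes) should not be reported as an SAE", so a patient who dies of progression before any contact could have no safety record. With 10 deaths assumed among 130 Part 2 patients, losing 2 would turn 10/130 = 7.7% into 8/128 = 6.3%. The documents do not support this as a main consequence:

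- Protocol 12.1 removes progression deaths from serious adverse event reporting, not from death recording. Sudden and unexplained deaths must still be reported as serious adverse events.
- SAP 4.2.5.1 refers to an eCRF death report page, and deaths are a subsection of the SAP's safety chapter. A recorded death would ordinarily count as safety information. The list of data types in SAP 5 is introduced as examples, so the absence of death from it proves little.
- SAP 5.2 plans an overview and a listing of all deaths, separate from deaths as an adverse event outcome. For Part 2, SAP 4.2.7.2 also gives the proportion who died, with an exact 95% interval, in mITT.
- If a death were not documented at all, deleting the condition would restore the patient to the denominator but not the death to the numerator, so 10/130 would not be recovered.
- Both the 10 deaths and the 2 lost are assumed.

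Nor is it an argument that the safety set then differs from mITT. The two differ by design, because mITT is restricted to Part 2 and to eligible or waived patients.

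**Conclusion.** The inconsistency is real, sits within each document, and is unresolved. The narrower definition selects the adverse event denominator on post-dose data, which the other sections neither state nor need. The practical size is probably very small: 64% would read 64.3% to 65.2% if 1 to 4 of about 209 treated patients had no later record. That range rests on an assumed k, since the documents give no estimate. The tempting extension, that early deaths drop out of reporting, is not established. Recorded deaths would ordinarily qualify the patient for the safety population and are summarised elsewhere as well. What remains there is only that the SAP does not say in words that a death record counts. This is a minor consistency correction, with no bearing on the primary response analysis.

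**What to change.** In protocol 13.2.1.3 and SAP 3.1.2, delete the second condition (the requirement for post-baseline safety information). The safety population is then all patients who received any amount of study treatment, as the synopsis, protocol 7.1, 13.1.1, 13.3.4 and 13.3.7, and SAP 1.1 already say. Patients without later data stay in the denominator.

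The cost is one phrase removed in two places and a denominator that may be slightly larger. No planned analysis is lost. If the sponsor prefers to keep the condition, the lesser alternative is to define the term, state that a death record satisfies it, align the other sections with it, and report how many treated patients it excludes.

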#### **13.2.1.4. Sub-group Efficacy Analyses**

The subgroup comparisons of interest will be evaluated per the Statistical Analysis Plan (SAP) (version 1.0).

### **13.3. Data Analysis and Presentation**

Summary tabulations will be presented separately for each study part and by penta-refractory MM patients and quad-refractory MM patients in Part 1 for disposition as noted above, and for demographic, baseline, efficacy and safety data as noted in the following sections. All data collected on the eCRF will be provided in by-patient data listings.

#### **13.3.1. Demographic Characteristics**

Demographic characteristics will be summarized for the mITT, PP, and Safety populations and will include gender, race, ethnicity (Hispanic origin), and age at time of consent. For gender, race, and Hispanic origin, the summary statistics will be the number and percentage of patients within each category. The categories for race will be those recorded in the database. For age at time of consent, the mean, median, minimum, maximum, and standard deviation will be provided for each group and the total sample.

#### **13.3.2. Baseline Characteristics and Medical History**

Baseline characteristics include: performance status, duration from initial diagnosis, response to previous therapy, types of prior therapy, and height/weight. Baseline data will be tabulated using summary statistics for the mITT, PP, and Safety populations; no formal hypothesis testing will be performed.

Medical history and physical examination results at baseline will be tabulated for the same analysis populations.

#### **13.3.3. Primary Endpoint**

The primary statistical analysis of efficacy will be performed on ORR (achievement of PR, VGPR, CR or sCR) for the mITT population. For the primary analysis of superiority to the minimal threshold ORR, analysis will be performed using a two-sided 95% confidence interval, calculated for the rate of ORR, and statistical significance will be declared if the lower bound of this interval is greater than 10%.

#### **13.3.4. Secondary Endpoints**

The following secondary efficacy endpoints will be analyzed separately for mITT and PP populations.

- Duration of response (DOR = Duration from first observation of at least PR to time of disease progression [PD] or death due to disease progression, whichever occurs first. DOR will be censored for death due to any causes other than disease progression.
- Clinical Benefit Rate (CBR = sCR + CR + VGPR + PR + minimal response [MR]), and duration of clinical benefit (Duration from first observation of at least

MR to time of disease progression or death due to disease progression, whichever occurs first. Duration of clinical benefit will be censored for death due to any causes other than disease progression)

- Disease Control Rate (DCR = CBR + stable disease [SD; for a minimum of 12 weeks])
- Progression Free Survival (PFS = Duration from start of study treatment to PD or death [regardless of cause], whichever comes first)
- Time to Progression (TTP = Duration from start of study treatment to time of disease progression) obtained with selinexor plus dexamethasone vs. TTP on most recent prior therapy
- Time to Next Treatment (TTNT = Duration from start of study treatment to start of next anti-MM treatment or death due to disease progression, whichever occurs first)
- Overall Survival (OS = Duration from start of study treatment to death)
- Quality of Life (QoL) using the Functional Assessment of Cancer Therapy - Multiple Myeloma (FACT-MM)

Time-to-event endpoints (including duration of response, PFS, TTP, and OS) will be assessed using Kaplan-Meier (KM) methods, including an estimate of the median, as well as the 25th and 75th percentiles, along with two-sided 95% CIs. Duration of CBR will be regarded as descriptive adjuncts to the analyses of response rates. Clinical benefit (CBR) and disease control (DCR) rates will be statistically evaluated using two-sided 95% confidence intervals.

QoL will be assessed using the Functional Assessment of Cancer Therapy-Multiple Myeloma (FACT-MM). This instrument combines the General version of the FACT (FACT-G) with a MM-specific subscale (14 items). The subscales for the FACT-G are Physical Well-Being (7 items), Social/Family Well-Being (7 items), Emotional Well-Being (6 items), and Functional Well-Being (7 items). The trial outcomes index (TOI; total of 41 items) will be the primary measurement of interest, comprised of the Physical and Functional subscales plus the MM-specific subscale. Each item is rated on a 5-point Likert scale, ranging from 0 (“Not at all”) to 4 (“Very much”), therefore the TOI has a score ranging from 0 to 120. The QoL assessment will be performed at Baseline (prior to first dose of study treatment), Day 1 of each cycle on or after the second, and at the Final visit. The QoL analysis will be based on changes in the total TOI score from Baseline using paired T-tests. A secondary analysis of QoL will be performed in a similar manner using the total of all subscales. All 5 individual subscale total scores will be summarized over time using descriptive statistics.

Additionally, the following analyses of safety and tolerability secondary endpoints will be performed on the overall population of patients who received any amount of study treatment, presented overall and by study part.

- Safety and tolerability using National Cancer Institute (NCI) Common Terminology Criteria for Adverse Events (CTCAE), v 4.03.
- Describe the PK properties of selinexor in this patient population (Part 1 only).

CCI [REDACTED]

[REDACTED]

[REDACTED]

[REDACTED]

[REDACTED]

[REDACTED]

[REDACTED]

[REDACTED]

[REDACTED]

### 13.3.6. Pharmacokinetic CCI [REDACTED] Data

Plasma samples will be analyzed via a validated high performance liquid chromatography/tandem mass spectrometry (HPLC/MS-MS) method for plasma selinexor concentration. Selinexor concentration data will be analyzed for Part 1 patients only in a non-linear mixed effects population PK model with potential covariates including, but not limited to: age, body weight, gender, disease state, baseline hepatic or renal function, concomitant medications, and treatment. CCI [REDACTED]

[REDACTED]

### 13.3.7. Safety Data

Safety analyses will be performed on the overall population of patients who received any amount of study treatment, presented overall and by study part, and separately for Part 1 penta-refractory MM patients, Part 1 quad-refractory MM patients, and Part 2 penta-refractory MM patients. The original dose level for each patient will be used for safety analysis; no separate categories for dose escalation or reduction will be conducted in the primary analysis of safety. CCI [REDACTED]

[REDACTED]

#### 13.3.7.1. Adverse Events

AEs will be coded using the Medical Dictionary for Regulatory Activities (MedDRA) and displayed in tables and listings using MedDRA system organ class (SOC) and Preferred Term (PT).

Analyses of AEs will be performed for those events that are considered treatment-emergent, where treatment-emergent is defined as any AE with onset, or worsening of a pre-existing condition, on or after the first dose of study treatment through 30 days following the last dose of study treatment, or any event considered drug-related by the Investigator through the end of the study. AEs with partial dates will be assessed using the available date information to determine if treatment-emergent; AEs with completely missing dates will be assumed to be treatment-emergent. No formal hypothesis-testing of AE incidence rates will be performed.

AEs will be summarized by patient incidence rates, therefore, in any tabulation, a patient contributes only once to the count for a given AE (preferred term). The number and percentage of patients with any treatment-emergent adverse events (TEAE) will be summarized for each treatment group, classified by SOC and preferred term. The number and percentage of patients with TEAEs assessed by the Investigator as at least possibly related to treatment will also be tabulated. The number and percentage of patients with any Grade  $\geq 3$  TEAE will be tabulated in the same manner.

The Investigator will judge the causal relationship between the occurrence of an AE and the study drug as not related, unlikely related, possibly related, or related. In the event a patient repeatedly experiences episodes of the same AE, then the event with the highest severity and/or strongest causal relationship to treatment will be used for purposes of tabulations.

All reported SAEs will be tabulated.

All AEs (treatment-emergent and post-treatment) will be listed in by-patient data listings, classified by treatment, patient and day on study. In addition, separate by-patient listings will be provided for the following: deaths; SAEs; and AEs leading to withdrawal.

